## 3.2 Overall Study Design and Plan

Details regarding the study design and plan for the Core Study and Extension Phase are in the Protocol. For a general overview, see the schema in [Section 13.1](#).

The Extension Phase will consist of a Maintenance Period (29 weeks) and a Follow-up Period (4 weeks).

All subjects who completed all scheduled visits up to and including Visit 9 in the Core Treatment Phase were eligible to participate in the Extension Phase of the study.

### Maintenance Period

During the Maintenance Period of the Extension Phase, all subjects were to continue with their optimal perampanel dose (ie, that dose level that they completed on during the Core Study). Multiple dose adjustment was allowed if a subject was experiencing intolerable AE(s) or a higher dose was deemed to be beneficial. The maximum dose of perampanel was 12 mg/day for subjects who were not receiving EIAEDs. For subjects who were receiving EIAEDs, the maximum dose was 16 mg except that for subjects enrolled in Japan, the maximum dose was 12 mg/day.

Addition, deletion, and dose changes to the concomitant antiepileptic drugs (AEDs) were allowed during Extension Maintenance Period. Conversion to monotherapy on perampanel was also permitted at the discretion of the investigator, if it was considered appropriate to control the seizures.

### Follow-Up Period

Follow-up was to be conducted 4 weeks ( $\pm 7$  days) after the last dose of study drug for all subjects.

## 4 DETERMINATION OF SAMPLE SIZE

As this was an extension study, it was not possible to accrue a predetermined number of patients; therefore, there was no a priori determination of sample size. The maximum possible number of subjects in Extension Phase is the total number of treated subject in Core Study.

## 5 STATISTICAL METHODS

All descriptive statistics for continuous variables will be reported using mean, standard deviation (SD), median, minimum and maximum. Categorical variables will be summarized as number (percentage) of subjects. All summaries will be produced by age cohort (4-<7 and 7-<12), disease cohort (POS, PGTC, GTC) and inducer status (inducer, non-inducer). All

analysis will be conducted for all subjects who have completed the core study and participated in the Extension Phase.

In general, the scope of endpoints and analyses will be based on data collected throughout the entire duration of perampanel exposure (i.e., Core and Extension).

### **Analysis for CSR in Japan**

For CSR in Japan, all analyses defined in this document will be repeated using all subjects enrolled in the study, including those who did not participate in the Extension Phase, and will also be repeated using subjects enrolled in Japanese sites only.

## **5.1 Study Endpoints**

### **5.1.1 Primary Endpoints**

Safety and tolerability, which include incidence of treatment-emergent adverse events (TEAEs) and SAEs, laboratory parameters, vital signs, and ECG parameters, of perampanel oral suspension in children (ages 4 to <7 years and  $\geq 7$  years to <12 years) with POS or PGTC

### **5.1.2 Secondary Endpoints**

The following endpoints will be analyzed:

1. The relationship between plasma levels of perampanel and efficacy endpoints (ie, change in average seizure frequency over 28 days, responder probability, and the proportion of subjects who are seizure-free in the Maintenance Period of the Core Study) separately for each seizure type
2. The relationship between plasma levels of perampanel and cognition endpoints including change from baselines in ABNAS, CBCL, and LGPT. In addition, depending on the AE data, the relationship between plasma levels of perampanel and select AEs will be assessed
3. Change from baseline at Week 23 and Week 52 in ABNAS, CBCL, and LGPT
4. Changes from baseline at Week 23 and Week 52 in growth and development parameters (height, weight, thyroid, and IGF-1)
5. Change from baseline in EEG and the frequency of EEG abnormalities during awake and sleep state
6. Proportion of subjects (aged 6 or older at time of consent/assent) with any treatment-emergent reports of suicidal ideation and behavior on the C-SSRS and intensity of

these behaviors assessed using C-SSRS scores

7. The median percent change in seizure frequency per 28 days during Treatment Phase (Titration Period and Maintenance Period) of the Core Study, and during the long-term treatment (up to 52 weeks) relative to the Pretreatment Phase. Seizure frequency will be based on the number of seizures per 28 days, calculated as the number of seizures over the entire time interval divided by the number of days in the interval and multiplied by 28
8. Proportion of responders (25% responders defined as a decrease in 28-day seizure frequency of equal or greater than 25% compared to baseline seizure frequency; 50% responders defined as a decrease in 28-day seizure frequency of equal or greater than 50% compared to baseline seizure frequency; 75% responders defined as a decrease in 28-day seizure frequency of equal or greater than 75% compared to baseline seizure frequency) during Maintenance Period of Core Study, and during the long term treatment (up to 52 weeks)
9. Proportion of subjects who are seizure-free during Maintenance Period of Core Study, and during the long-term treatment (up to 52 weeks)
10. CGI of Change

### 5.1.3 Exploratory Endpoint

Change from baseline at Week 23 and Week 52 in EQ-5D-Y

## 5.2 Study Subjects

### 5.2.1 Definitions of Analysis Sets

The **Safety Analysis Set** is the group of subjects who received at least 1 dose of study drug in the Extension Phase and had at least one postdose safety assessment in the Extension Phase.

The **Full Analysis Set (FAS)** is the group of subjects who received at least 1 dose of study drug in the Extension Phase and had at least 1 postdose seizure measurement in the Extension Phase.

The **Enrolled Subjects** will consist of all subjects who chose to participate in the Extension Phase.

For CSR in Japan, the analysis sets defined in Core Study SAP will be used.

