### 5.3.6 Other Considerations

#### 5.3.6.1 Safety

A subject who has an AE coded to the same preferred term more than once during the Extension Phase and the Core Study will be counted only once in the incidence calculations for that AE. Similarly, if a subject has more than one AE in a single system organ class (SOC), the incidence will be counted only once for that SOC. If a subject has the same AE more than once, the occurrence that is of greatest severity will be used in the calculation of the incidence of individual AE by severity. The AE considered most closely related to study treatment will be used in the calculation of incidence of individual AE by relationship.

If a subject has taken the same concomitant medication (as coded to preferred WHO-drug term) more than once, the subject will be counted only once in the tabulation.

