#### 5.4.2 Secondary Efficacy Analyses

The percent change in seizure frequency per 28 days during the Core Study and Maintenance Period of the Extension Phase with respect to baseline assessment collected during the Pretreatment Phase of the Core Study will be summarized using descriptive statistics (n, mean, median, minimum, maximum and 95% confidence interval). The percent change in seizure frequency per 28 days are calculated for total seizure, POS total seizure and total complex partial seizure for POS cohort, for PGTC seizure, absence seizure, myoclonic seizure and total seizure for PGTC cohort and for Secondarily Generalized seizures for GTC cohort. Total Seizures is sum of all seizures, including POS, generalized and other seizures. Total POS Seizures is sum of all POS seizures, including simple partial seizures without motor signs, simple partial seizures with motor signs, complex partial seizures and complex partial seizures with secondary generalization. Secondarily Generalized seizures cohort is a subset of POS cohort.

The proportion of subjects who are seizure-free and the proportion of responders based on decrease from baseline (during the Pretreatment Phase) in 28-day seizure frequency of equal or greater than 25%, equal or greater than 50%, and equal or greater than 75% during Maintenance Period of the Extension Phase will be summarized using frequency count (number and percentage). If subjects complete the Extension Phase and have no seizure during the Maintenance Period, those will be treated as seizure-free.

The number of subjects with new seizure types compared to Baseline Period and Seizure history will be summarized.

The CGIC and CGIS will be summarized for each visit using frequency count (number and percentage).

For Japan submission, all of the analysis will be repeated for Japanese population.

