## 5.6 Safety Analyses

All safety analyses will be performed on the Safety Analysis Set. Safety data will be summarized on an “as treated” basis using descriptive statistics (eg, n, mean, standard deviation, median, minimum, maximum for continuous variables; n [%] for categorical variables). Safety variables include TEAEs, clinical laboratory parameters, vital signs, 12-lead ECG results, C-SSRS, growth parameters, CBCL, LGPT, and EEG. Study Day 1 for all safety analyses will be defined as the date of the 1st dose of study drug.

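### The Extension SAP's cumulative safety tables count events from the first Core dose but only in children who entered the Extension, so deaths and AE discontinuations that happened in Core cannot appear in them

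*SAP*

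**What the plan says.** The SAP file holds a Core SAP and an Extension SAP. By main Extension analysis I mean everything in the Extension SAP except the repeats for the Japan CSR.

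- **Window.** Extension SAP Section 5 says the scope of analysis "will be based on data collected throughout the entire duration of perampanel exposure (i.e., Core and Extension"). Section 5.6.2 starts the TEAE window at the first Core dose, and Section 5.6.6 does the same for the C-SSRS.
- **Set.** Section 5.6: "All safety analyses will be performed on the Safety Analysis Set". Section 5.2.1 limits that set to children who "received at least 1 dose of study drug in the Extension Phase and had at least one postdose safety assessment in the Extension Phase".
- **Entry.** Section 3.2: "All subjects who completed all scheduled visits up to and including Visit 9 in the Core Treatment Phase were eligible" for the Extension.
- **Tables.** Section 5.6.2 tabulates on that set TEAEs, SAEs, TEAEs leading to death and TEAEs leading to discontinuation. It also analyses AEs by actual dose at onset.
- **Japan CSR.** Under Section 5, all analyses "will be repeated using all subjects enrolled in the study, including those who did not participate in the Extension Phase", with a further repeat on Japanese sites only. Section 5.2.1: "For CSR in Japan, the analysis sets defined in Core Study SAP will be used".
- **Core SAP.** It covers the core phase only. Sections 5.2.1 and 5.6.2 tabulate deaths, SAEs and AE discontinuations on all treated children with a postdose safety assessment, and provide listings.
- **Protocol Appendix 1.** It pairs the same Extension A safety set with the same Core plus Extension A window.

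**The concern.** A table that starts at the first dose and runs through the Extension looks like cumulative incidence in the children who were treated. Here it is cumulative incidence in those who completed Core and continued. For death and AE discontinuation, the events that removed children during Core are exactly the ones left out.

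Safety and tolerability is the primary endpoint, and the suicidality objective is stated for 52 weeks. The titration period lies wholly before rollover, so children who stopped during it are absent. AEs in general by dose at onset appear only in the Extension SAP; the Core SAP plans dose at onset only for falls (AEs of special interest). That analysis therefore has no all-treated version outside the Japan CSR.

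The table shells are a separate document, so the labelling is unknown. The SAP text does not ask for a note on the tables that they are conditional on rollover.

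**Working it through.** The plan gives no figure to reproduce here, and no dropout, AE-stop or rollover rate. Steps 1 to 3 need no rates. Steps 4 to 6 are illustrations on assumed rates, with N = 160 taken from the planned sample size.

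**1. Membership.** Being in the set requires an Extension dose and an Extension assessment. Entry requires all visits through Visit 9. A child who died in Core, or stopped study drug in Core for an AE, meets neither condition. Such children contribute exactly 0 to the cumulative tables.

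**2. What the zero covers.** It covers deaths and stops that happen in Core. An AE that starts in Core and leads to stopping in the Extension is still counted.

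**3. Can a reader add the two reports?** Not from the TEAE or SAE tables. Under Section 5.3.6.1, a child who has one AE coded identically "more than once during the Extension Phase and the Core Study will be counted only once in the incidence calculations for that AE". Suppose 24 children stop in Core and 136 roll over, and an event occurs in 6 stoppers, in 30 rollovers during Core, and first in the Extension in 10 more rollovers.
- Core table: (6 + 30)/160 = 36/160.
- Main Extension table: (30 + 10)/136 = 40/136.
- Adding the tables: 36 + 40 = 76, with 30 children counted twice.
- Correct count from subject-level listings: 40 + 6 = 46/160 = 28.8%.

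**4. Counts and percentages.** Let m children not roll over, a of them stopping for an AE in Core; let n roll over, x of them stopping later for an AE. The main table shows x/n; all-treated is (a + x)/(m + n). The count is understated by a whenever a > 0. The percentage is understated only if a/m > x/n. With every completer rolling over:

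| Core stops m | for AE, a | rollovers n | later AE stops x | main table | all treated |
|---|---|---|---|---|---|
| 16 | 0 | 144 | 6 | 6/144 = 4.2% | 6/160 = 3.8% |
| 16 | 8 | 144 | 3 | 3/144 = 2.1% | 11/160 = 6.9% |
| 24 | 12 | 136 | 4 | 4/136 = 2.9% | 16/160 = 10.0% |
| 32 | 22 | 128 | 5 | 5/128 = 3.9% | 27/160 = 16.9% |

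One Core death reads 0 in the main table against 1/160 = 0.6%. One Extension death with none in Core reads 1/144 = 0.7% against 1/160 = 0.6%.

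**5. Is the gap only a follow-up artefact?** Assume weeks on drug of 8 for Core stoppers, 37.5 for later AE stoppers (midpoint of 23 and 52) and 52 for other rollovers, with 52.18 weeks per year. For the second row, rollover exposure is (141 × 52 + 3 × 37.5)/52.18 = 142.7 subject-years, and Core stoppers add 16 × 8/52.18 = 2.5, giving 145.1 after rounding. Rates per 100 subject-years:
- Row 2: 3/142.7 = 2.1 against 11/145.1 = 7.6.
- Row 3: 4/134.4 = 3.0 against 16/138.1 = 11.6.
- Row 4: 5/126.2 = 4.0 against 27/131.1 = 20.6.

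Varying the 8 weeks from 4 to 16 moves the all-treated rates only to 7.6–7.5, 11.7–11.3 and 21.0–19.9. The gap in those rows is not a matter of follow-up time.

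**6. Other TEAEs.** With 20% stopping in Core and 20% incidence in rollovers, all-treated incidence is 0.2 × 0.5 + 0.8 × 0.2 = 26% if stoppers have 50% incidence, and 0.2 × 0.1 + 0.8 × 0.2 = 18% if they have 10%. Direction is open.

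**The case against.** The strongest reply is that the plan does what the protocol says and does it openly. Protocol Appendix 1 defines this set and this window, and Extension SAP Section 5 states that the analyses are for Core completers who entered the Extension. The Core SAP reports Core deaths, SAEs, AE discontinuations and C-SSRS findings on all treated children. It also summarises discontinuation at the maximum dose (Section 5.6.1) and TEAEs by speed of titration (Section 5.6.2), so dose information on titration stoppers is not absent. All of this stands. A reader might infer that safety events are lost or hidden, or that the SAP departs from the protocol; the documents support neither.

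It can also be said that the all-treated cumulative tables already exist in the plan. They do, and the Japan repeat covers every enrolled child. Reading it as limited to Japanese children would be wrong, because the Japanese-sites repeat is a separate one. The remaining gap is that these tables are assigned only to the Japan CSR.

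Finally, the size rests on assumed rates, and the first row of the table shows the percentage can go the other way. That stands too. It does not touch step 1, and the Core analyses just named do not replace AEs in general by dose at onset.

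**Conclusion.** The point holds as a choice of analysis set, not as an error or a breach of protocol. It should be addressed, but it is not critical. Core deaths and Core AE discontinuations cannot appear in the main cumulative tables, and this needs no assumption. Whenever such events occur, those counts understate the all-treated counts. The other cumulative safety summaries are conditional on rollover, with bias possible in either direction.

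A reader might infer that the percentages are always too favourable. They are not: that depends on whether AE stopping was proportionally more common in children who did not roll over than in those who did. The real size cannot be computed from the documents.

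A reader might also extend the point to efficacy, since "The percent change in seizure frequency per 28 days during the Core Study and Maintenance Period of the Extension Phase" is summarised on the rollover population as well. That is a separate question from the safety one and is not part of this conclusion.

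**What to change.** In the main Extension report, also present the all-subject cumulative safety tables already planned for the Japan CSR, on the Core Safety Analysis Set: deaths, AE discontinuations, TEAEs, SAEs, AEs by dose at onset, and C-SSRS. Give exposure-adjusted rates with the AE tables, because follow-up differs. Extension SAP Section 5.6.1 ends total exposure at the last Extension dose; for children who did not roll over, end it at the last Core dose, as in Core SAP Section 5.6.1.

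Keep the protocol-named Extension A set for the rollover tables, and state on each that it is conditional on completing Core and entering Extension A. Record the addition in Extension SAP Section 7.

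Cost: wording in Extension SAP Sections 5, 5.2.1, 5.6.1, 5.6.2 and 7. The tables are already to be programmed, so the new work is the exposure-adjusted rates, the exposure end date and the footnotes. Nothing is replaced. The downsides are two denominators in one report and possibly less favourable death and AE-discontinuation figures.

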### 5.2.2 Subject Disposition

The frequencies of completion, discontinuation, ongoing and the primary and other discontinuation reasons will be summarized using incidence rate (number of subjects and percentage).

### 5.2.3 Protocol Deviations

Not applicable.

### 5.2.4 Demographic and Other Baseline Characteristics

Demographic and other baseline characteristics for the Safety Analysis Set will be summarized using descriptive statistics. Continuous demographic and baseline variables include age, weight, height, and BMI; categorical variables include sex, age group (4-7, 7-12), race and ethnicity.

## **MEDICAL HISTORY**

The number (percentage) of subjects in the Safety Analysis Set reporting a history of any medical condition, as recorded on the CRF, will be summarized. A subject data listing of medical and surgical history will be provided.

Epilepsy-specific medical history for the Safety Analysis Set will be summarized using descriptive statistics, including time since diagnosis, suspected localization of the epileptogenic region and seizure type.

### 5.2.5 Prior and Concomitant Therapy

Concomitant medications are defined as medications that (1) started before the first dose of perampanel at Core Study and were continuing at the time of the first dose of perampanel, or (2) started on or after the date of the first dose of perampanel (or, started at the time of or after the first dose of perampanel) up to 14 days after the subject's last dose.

Concomitant medications taken during the study will be coded using the World Health Organization Drug Dictionary (WHO-DD) and further coded and summarized by Anatomical Therapeutic class, pharmacological class, pharmacological subclass, and WHO drug term.

A summary of concomitant AEDs, including the number of subjects who take concomitant enzyme inducing antiepileptic drugs (EIAEDs), will be produced. A shift table of number of AEDs from baseline to the end of treatment will also be produced.

### 5.2.6 Study Medication Treatment Compliance

In general, study medication treatment compliance (%) for a given period of time will be calculated as follows with respect to (*i.e.*, within) the given period of time:

$$\text{Study Medication Treatment Compliance (\%)} = \frac{(\text{Study Med issued in grams} - \text{Study Med Returned in grams})}{(\text{Number of Days} \times \text{Prescribed Daily Dose in ml}) \times \text{Suspension density of 1.07g/ml}} \times 100$$

Study medication treatment compliance (%) will be presented for the SAS by visit in the Maintenance Period of Extension Phase. Subjects will also be categorized by compliance categories of <80%, 80%-120% and >120%.

### 5.3 Data Analysis General Considerations

#### 5.3.1 Pooling of Centers

Subjects from all centers will be pooled for all analyses. For analysis specifically planned for Japan subjects, only Japan centers will be pooled.

#### 5.3.2 Adjustments for Covariates

Not applicable.

#### 5.3.3 Multiple Comparisons/Multiplicity

Not applicable.

#### 5.3.4 Examination of Subgroups

The efficacy seizure endpoints will be summarised by disease cohorts (POS, PGTC, and GTC). Within the POS and PGTC disease cohorts, endpoints will also be summarized by age cohort (4 to <7 years, ≥7 to <12 years), and the presence or absence of concomitant EIAEDs,

All other endpoints will be summarised by disease cohorts (POS, PGTC, and GTC), age cohort (4 to <7 years, ≥7 to <12 years), and with or without use of concomitant EIAEDs.

#### 5.3.5 Handling of Missing Data, Dropouts, and Outliers

The algorithm on the assumptions used for imputing the missing dates for AEs is given in the programming specifications.

If the day and month are missing, events will be considered treatment-emergent if the year is equal to or after the year of the first dose date; if days are missing, events will be considered treatment-emergent if the year is after the year of the first dose, or if the year is equal to the year of the first dose date and the month is equal to or after the month of the first dose date.

For the purpose of summarizing maximum severity, if the severity of an adverse event (AE) is missing for a subject, then, if this subject has another AE with the same preferred term that has “severe” severity, the maximum severity of the AE will be noted as “severe”; otherwise the maximum severity will be noted as missing. Similarly, for the purpose of summarizing the closest relationship in AE causality, if the relationship of an AE to study drug is missing,

the AE will be noted to be probably related if there is another probably related AE with the same preferred term, otherwise this relationship will be noted as missing.

For determining treatment emergent markedly abnormal lab values, a missing baseline lab value will be assumed to be of grade 0.

The algorithm to impute missing dates for concomitant medications is given in the programming specifications. No special handling of missing data is planned for the analysis of any of the other safety variables.

Data exceptions or outliers will be determined by inspection of the tables, listings, and graphs in consultation with the clinical study team. The effect of outliers on analyses may be assessed by re-analyzing the data without the outliers.

All the listings will display the original missing values.

